5.1 Participant Inclusion Criteria

To be eligible to participate in this study, an individual must meet all the following criteria:

- Female
- 40 to 74 years old
- Able to undergo the informed consent process
- Willingness to comply with all study procedures
- Available for the duration of the study
- In good general health and at average risk for developing breast cancer

5.2 Participant Exclusion Criteria

An individual who meets any of the following criteria will be excluded from participation in this study:

- Male*
- Currently diagnosed or are receiving treatment for breast cancer
- Have an uninvestigated area of suspicion or concern in their breast

*Note: While Namida Lab, Inc. understands that breast cancer also affects men, there are not enough samples in the repository from men with breast cancer to ensure the accuracy of the results of Melody® for men.

5.3 Strategies for Recruitment and Retention

Target sample size:

- An a priori power analysis was conducted using G*Power v3.1.9.2 to determine the minimum sample size required to find significance with a desired level of power set at 0.80 and alpha (α) level at 0.05. Based on this analysis, it was determined that a **minimum of 205 participants** were required to ensure adequate power for a Pearson's Chi-square Test of Independence. (12, 13, 14)

The anticipated site participants' accrual rate will vary; all sites and participants will be located within the United States. Participants will be recruited from outpatient clinics, larger employers, and/or the general public. Participant recruitment venues are site-specific, for example, outpatient clinic monthly clinical breast exam events. Potential participants will be identified and approached using inclusion/exclusion criteria and site-specific events and/or communication channels.

While exact recruitment methods will be specific to each site, the material will be made available in versions suitable for flyers, email, post through social media, or distributed by mail. Forward-facing participant recruitment materials have been submitted separately with indications on how it can be personalization to each site.

The VIOLA Study participants are all women due to the development and validation of Melody®. The objectives and endpoints encourage minorities, employee volunteers, economically disadvantaged, and/or a medically underserved population to participate in the VIOLA Study. The justification for involving vulnerable populations is because they are primarily affected by disparities in the healthcare system. Employee volunteers are included because study sites provide current medical care and have a trusted relationship with the employee volunteer as a current patient.

Careful considerations have been included in the study design and recruitment process to ensure minimal harm/risks and maximum participant protection. Participants will have access to translated study materials and access to additional healthcare navigation if needed. Employers will not be notified of study participation or Melody® results; participation or nonparticipation is confidential. Each participant will receive a \$25 Walmart gift card when completing the VIOLA Study, and there is no cost to participate.

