- US Code of Federal Regulations applicable to clinical studies (45 CFR 46)
- ICH GCP E6
- Completion of Human Subjects Protection Training

Protocol Summary

Title: Validating Individualized breast cancer screening by Offering a new Link in Access

Short Title: The VIOLA Study

Précis: The VIOLA Study is a Clinical Utility Study to investigate the useability of Melody®, a tear-based screening assay for breast cancer developed and validated by Namida Lab, Inc., a high complexity CLIA certified lab.

The VIOLA Study will have multiple study sites, with a minimum participation of 205 women who are 40 to 74 years of age, at average risk for developing breast cancer, asymptomatic, and have no concerns or breast abnormalities.

Melody® consists of two parts: tear sample collection and clinical lab assay. Participants will have a tear sample collected at a study site. The clinical lab assay, Melody®, will be performed at Namida Lab, Inc. The results of the Melody® assay will be returned to the site clinician to be discussed with the participant.

Objectives: Primary Objective: Investigate the clinical utility of Melody® in federally qualified health centers in populations with historically low compliance rates with screening mammography.

Secondary Objective: Assess how incorporating Melody® into a primary care provider setting affects participation and confidence in the current breast health continuum of care.

Endpoint: Primary endpoint: The VIOLA Study is designed to quantify the relationship between two variables: an exposure and an outcome, by utilizing different study sites and recruiting from a diverse population.

Secondary endpoint: Quantifying the relationship between Melody® and increased participation in breast health care offers the clinical utility evidence required for adoption into the Standard of Care.

Population: Women ages 40-74 years old, at average risk for developing breast cancer

Number of Sites: 3+ sites

Study Agent: Melody® is a tear-based, high complexity lab-developed test. Melody® has been developed, validated, and will only be run by Namida Lab, Inc. as a tool in breast cancer screening.

Study Duration: 6-12 months

Participant Duration: Six months

Schematic of Study Design

The VIOLA Study: Validating Individualized breast cancer screening by Offering a new Link in Access

Define – Month 1-6 Study Design/Site Enrollment

- Recruit and consent study sites
- Establish study site principal investigator and study agreement consent

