4.2 Study Endpoints

4.2.1 Primary Endpoint

It is common knowledge that disparities exist in breast health, preventative care, and screening mammography. Namida Lab, Inc. knows the potential of Melody® to be a tool that bridges the gap between underserved populations and positive health outcomes. The administration of Melody® does not require additional appointments or trips and can be done by any member of a medical team.

As such, Namida Lab, Inc. is partnering with federally qualified health centers and large employers to evaluate the clinical utility of Melody®. Do women in populations with historically low compliance rates with screening mammography, who receive Melody® as the first step in the breast health continuum of care, participate in screening mammograms at higher rates than previous years?

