 Contraceptive Patch
 Intrauterine device (IUD)
 Vaginal Ring
 None
2. Are you currently using any hormone replacement therapy? (select one)
 Yes No
3. Please select what hormones you are currently taking: (select all that apply)
 Testosterone
 Estrogen
 Progesterone
 Other: _____
4. Hormone replacement medication name if known: _____
5. At what age did your periods begin? _____ (number)
6. Do you still have regular periods? (select one)
 Yes No
7. If you Do Not have regular periods, please select one of the following reasons: (select one)
 Menopause
 Hysterectomy
 Response to Birth Control
 Uterine Ablation
 Other (please describe): _____
 Unknown
8. Do you still have ovaries? (select one)
 Yes No

Section 3: Breast health:

1. Have you ever been told you have dense breast tissue? (select one)
 Yes No
2. Are you currently on, or have you been told, you should be on a high-risk breast cancer screening protocol? (select one)
 Yes No

3. Do you get an annual mammogram for breast cancer screening? (select one)
 Yes No
4. Do you get a bi-annual, every two years, mammogram for breast cancer screening? (select one)
 Yes No
5. When was your last screening mammogram? (enter date or select one)
(mm/dd/yyyy) ____/____/____ Unknown N/A
6. Have you ever received an abnormal screening mammogram? (select one)
 Yes No
7. From your last mammogram, what BI-RADS assessment category was on your mammogram results report? (select one)
 0 - Incomplete - Additional imaging evaluation and comparison to prior mammograms are needed.
 1 - Negative
 2 - Benign (non-cancerous findings)
 3 - Probably benign finding (follow-up in a short time frame is suggested)
 4 - Suspicious abnormality (biopsy should be considered)
 4A - Finding with a low likelihood of being cancer (more than 2% but no more than 10%)
 4B - Finding with a moderate likelihood of being cancer (more than 10% but no more than 50%)
 4C - Finding with a high likelihood of being cancer (more than 50% but less than 95%), but not as high as Category 5
 5 - Highly suggestive of malignancy (appropriate action should be taken)
 6 - Known biopsy-proven malignancy (appropriate action should be taken)
 Unknown

Section 4: Personal history and family history of cancer:

1. Please list below any cancers you have or have had in your lifetime.

No personal history of cancer Personal history unknown

Cancer Type	Year of diagnosis	Treatment	Treatment ongoing

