Provider: [name], MD
Collecting Location: Namida Lab
Sample ID: MEL21000026
Entered by: [name]

Melody Test

Approved By: [name]

Melody Score **-0.509**

Reference Range:

Melody Score Interpretation **Low**

04/16/21 10:41 AM Melody® is an adjunct clinical test that is intended to be based on the independent medical judgment of the ordering physician in conjunction with the patient's complete medical history and the result of standard care testing. It is recommended that a Melody score above 0.1 be clinically correlated with a structural examination of the breast tissue such as mammography.

Melody is not a replacement for a screening mammogram.

Melody Test type: Composite algorithmic analysis of tear protein biomarkers. Quantitative values of individual biomarkers are not reportable and are not associated with individual biomarker result reference ranges.

Precautions and Limitations:
Melody is intended for women ages 40-87 at average risk of developing breast cancer.

Melody may produce a false positive or false negative result. A Melody score below 0.1 does not guarantee the absence of breast cancer. Patients with a Melody score below 0.1 should be advised to continue participating in breast health standard care testing for their age group. A Melody score above 0.1 does not guarantee the presence of breast cancer. Patients with a Melody score above 0.1 should be referred for imaging.

Melody was developed and its performance characteristics determined by Namida Lab, Inc. It has not been cleared or approved by the U.S. Food and Drug Administration. The FDA has determined that such clearance is not necessary. This test is used for clinical purposes. Namida Lab, Inc. is regulated under the Clinical Laboratory Improvement Amendments of 1988 (CLIA) as qualified to perform high-complexity clinical testing.

J. Study Participant Exit Survey/Questionnaire

**VIOLA Study:
Validating Individualized breast cancer screening
by Offering a new Link in Access**

Study Participant Exit Survey

Thank you for taking the time to participate in our study. Please answer the following questions to the best of your knowledge.

Last Name: _____ First Name: _____ Middle Initial: _____

Date of Birth (mm/dd/yyyy) ____/____/____

1. Before enrolling in the VIOLA Study, did you have an appointment for a screening mammogram?
 Yes No

2. How comfortable were you with the sample collection process? (circle one)

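### The Summary, section 4.2.1 and section 5.3 name different target populations, and neither eligibility nor the primary analysis separates recruits by source or prior screening, so recruitment mix can raise or dilute the apparent effect.

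*Protocol*

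**What the plan says.** Three places in the protocol describe whom the primary question is about.

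- **Protocol Summary, primary objective:** "Investigate the clinical utility of Melody® in federally qualified health centers in populations with historically low compliance rates with screening mammography".
- **Section 4.2.1, primary endpoint:** the question opens "Do women in populations with historically low compliance rates with screening mammography", but the same section says that "Namida Lab, Inc. is partnering with federally qualified health centers and large employers to evaluate the clinical utility of Melody".
- **Section 5.3, recruitment:** "Participants will be recruited from outpatient clinics, larger employers, and/or the general public".

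The inclusion criteria in 5.1 cover sex, age, consent, willingness, availability, and a last item: "In good general health and at average risk for developing breast cancer". The exclusions in 5.2 are male sex, current breast cancer or its treatment, and one more: "Have an uninvestigated area of suspicion or concern in their breast". Neither list mentions health-center care, underserved status or past screening.

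The surveys do collect screening history. Appendix D asks "Do you get an annual mammogram for breast cancer screening", then about two-yearly mammograms and the date of the last one. Appendix J asks "Before enrolling in the VIOLA Study, did you have an appointment for a screening mammogram". Section 10.1 also foresees participants with a mammogram already scheduled.

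Sections 10.3 and 10.4.2 break the primary endpoint down by ethnicity, race, income band and metropolitan status. Section 10.1 makes the Arkansas 2019 rate the comparator. The secondary analysis (10.3, 10.4.3) compares each site with the 2019 rate which that site reports.

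**The concern.** Section 4.1 gives Melody to every participant, so there is no concurrent group drawn from the same recruits. Whatever sets the recruits apart from the women behind the 2019 rate enters the estimated effect. A woman who has a mammogram every year and had one booked before enrolment counts toward the VIOLA rate just like a woman who had never attended.

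The protocol's own rationale suggests that source matters. Section 2.2 says that uninsured women and women without usual care report the least mammography. Section 5.3 justifies including employee volunteers on the ground that the study sites already provide their care. Sources may therefore differ in baseline screening, and the primary analysis does not separate them.

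At stake is what the trial can conclude. A favourable result in a mixed sample need not describe the women in the Summary objective. An unfavourable one could hide a real effect in them.

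**Working it through.** **1. The text side by side**

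| Place | Population or setting |
|---|---|
| Summary objective | Health centers; low-compliance populations |
| 4.2.1 | Low-compliance populations; health centers and large employers as partners |
| 5.3 | Outpatient clinics, larger employers and/or general public |
| 5.1 and 5.2 | No rule on setting or screening history |
| 10.3 and 10.4.2 | Four demographic classes; no recruitment source, no prior screening |

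Employers appear in 4.2.1 and 5.3 but not in the Summary objective. The general public appears only in 5.3.

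**2. The plan's own effect size (Appendix L)**

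Inputs: 50% versus 70%, two-sided alpha 0.05, power 0.80, equal groups.

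n per group = [1.960 × √(2 × 0.6 × 0.4) + 0.8416 × √(0.25 + 0.21)]² / 0.20² = (1.358 + 0.571)² / 0.04 = 93.

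Total 186; 186 × 1.1 = 204.6, so 205, as stated. The sample size is not in dispute. It supplies the 20-point planning effect used as a yardstick below.

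**3. Dilution of a true effect (assumed mix)**

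Let f be the share of regular screeners, whose rate r Melody does not change. The others move from 50% to 70%. The pooled effect is 20 × (1 − f) points. With r = 90%:

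| f | Without Melody | With Melody | Effect | Power at 93 per group |
|---|---|---|---|---|
| 0 | 50% | 70% | 20 points | 0.80 |
| 25% | 60% | 75% | 15 points | 0.59 |
| 50% | 70% | 80% | 10 points | 0.35 |

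For r from 80% to 95%, power is 0.57 to 0.60 at f = 25% and 0.32 to 0.37 at f = 50%. These powers use Appendix L's two-group layout, the only one the protocol sizes.

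**4. Shift with no Melody effect (assumed mix)**

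The comparator is the statewide rate, so the shift must be measured against that. Let h and e be the screening rates of health-center women and of other recruits, each minus the state rate, and let f now be the share of other recruits. Shift = (1 − f) × h + f × e. Take a 20-point gap between the sources and place the state rate in two different positions:

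| f | h = 0, e = +20 | h = −10, e = +10 |
|---|---|---|
| 25% | +5 | −5 |
| 50% | +10 | 0 |
| 75% | +15 | +5 |

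The same gap and the same share can give inflation, no shift or a deficit. The documents give none of f, r, h or e.

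**The case against.** Much can be said for the plan as written.

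- **Employers are a stated part of the evaluation.** Section 4.2.1 names them, and 5.3 gives a reason for including employee volunteers. This stands. For employers the fault is that the Summary is narrower than 4.2.1 and 5.3, not that 5.3 departs from the endpoint. Only the general public is absent from both objective and endpoint.
- **The sample is not simply pooled.** The primary hypotheses are examined by location, income, race and ethnicity, and the secondary analysis gives each site its own comparison with its own 2019 rate. This stands in part. Income and metropolitan status are imperfect proxies for source. The site comparison is secondary, venues are chosen site by site, and neither analysis uses prior screening.
- **An analysis plan not shown here may use the baseline items.** Possibly, so their absence from planned subgroups is not in itself the point. But target population, eligibility and recruitment belong in a protocol, and 10.3 and 10.4.2 already fix the primary classes without these items.

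A reader might infer that employer and public volunteers already screen regularly. The documents do not say so. They fail to exclude such women and foresee that some had appointments. A reader might also infer that mixing sources must inflate the result against 2019. Step 4 shows otherwise: if health-center women screen below the state rate, adding other women first moves the sample toward the comparator.

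**Conclusion.** The point holds in this form: three sections name three different target populations, no eligibility rule or primary class ties the analysis to any of them, and the comparison is uncontrolled. Recruitment mix can raise the apparent effect or dilute a true one. Under the assumption that half the recruits are regular screeners whom Melody does not affect, a 20-point effect becomes 10 points. A shift in the absence of any effect could run in either direction, and the protocol gives no basis for a single figure.

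Two stronger steps are tempting and should not be taken. One is to test women not recently screened and without an appointment against the 2019 rate. That rate covers all women, including regular screeners, so the test would be biased against Melody. It would also change the question, since 4.2.1 asks about women in low-compliance populations, not individually overdue women. The other is to argue that a single-sample comparison with a fixed rate needs so few women that a restricted set keeps adequate power. The 50% and 70% in Appendix L belong to a two-group calculation, and nothing supports 50% as the reference rate for such a subgroup.

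The change is worth making because it is cheap and decides what the trial may claim.

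**What to change.** 1. Make the Summary objective, 4.2.1 and 5.3 agree on one target population. If employers and the general public belong to it, the objective should say so; if they do not, 4.2.1 and 5.3 should describe their role.
2. In 10.3, add recruitment source (health center, employer, general public) as a recorded field. In 10.4.2, report the primary participation rate separately for each.
3. Limit any conclusion about underserved or low-compliance women to the recruits who fit that description.
4. Within each source, tabulate participation with confidence intervals by mammogram in the past 12 months (from the last-mammogram date in Appendix D) and by appointment before enrolment (Appendix J).
5. Report the not-recently-screened, no-appointment group as an estimate, or compare it only with a 2019 rate for similar women. Do not test it against the all-women rate.

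The cost is revised wording, one new field and one table. Groups will be smaller and intervals wider, and the protocol offers no assurance of power within them. The appointment item sits on the exit survey, so it relies on recall and will be missing for women who do not complete that survey; the table should show how many.

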5.4 Participant Withdrawal or Termination

5.4.1 Reasons for Withdrawal or Termination

Participants are free to withdraw from the study at any time upon request. The sponsor-investigator or site-investigator may terminate a participant in the study if:

- Any clinical adverse event (AE), laboratory abnormality, or other medical condition or situation that occurs as continued participation in the study would not be in the participant's best interest.
- The participant meets an exclusion criterion (either newly developed or not previously recognized) that precludes further study participation.
- The participant fails to follow directions for participating in the study.
- The study is canceled and/or for administrative reasons.

5.4.2 Handling of Participant Withdrawal or Termination

Participants may request to withdraw from the study at any time. Participants that choose to withdraw early from the study will be voluntarily surveyed for reasons for withdrawal. The site investigator should advise the participant if any safety procedures are recommended and determine if the participant is willing to complete those along with any other end of study activities.

Participants will be asked for permission to continue to utilize the data collected after the point of

withdrawal for study purposes. If they decline, all data past the note of withdrawal will be deleted from the record system. However, please note that the FDA requires that any information collected up to participant withdrawal cannot be removed from the study.

Participants that are employed by a study site are under no obligation to participate in the study. Employees may withdraw from the study at any time and for any reason. Neither the decision to participate in the study nor any decision to withdraw will affect performance appraisal or employment. Any employee may refuse to participate or may withdraw from the study at any time without penalty or anyone blaming the employee.

5.4.3 Withdrawal Process in Mobile App

Participants will have the option to withdraw from the study by tapping a "Withdraw from Study" button within the app. This action will disable notifications and will result in a cessation of data collection. If a participant calls the study site requesting withdrawal from the study, the study personnel will instruct the participant on initiating withdrawal on the app. It will not be possible for any party other than the participant to withdraw from the study within the app.

In the few cases where the participant has received a notification and has initiated contact with the study personnel and then selects "Withdraw from Study" on the app, they may still receive follow-up communication from the study personnel. In order to stop further communication, these participants would need to inform the site personnel that they wish to be withdrawn.

5.5 Premature Termination or Suspension of Study

This study may be suspended or prematurely terminated if there is sufficient reasonable cause. If the study is prematurely terminated or suspended, the sponsor-investigator will promptly inform the IRB and provide the reason(s) for the termination or suspension. Site investigators can request suspension of the Namida Lab, Inc. app to stop the research. The study may resume once concerns about safety, protocol compliance, data quality is addressed and satisfy the sponsor, IRB, and/or FDA.

Circumstances that may warrant termination or suspension include, but are not limited to:

- Determination of unexpected, significant, or unacceptable risk to participants
- Demonstration of efficacy that would warrant stopping
- Insufficient compliance to protocol requirements
- Data that are not sufficiently complete and/or evaluable
- Determination of futility

6. Study Agent

